	
Dose adjustment may also take place beyond Week 6 based on results of transthoracic echocardiogram (TTE), stress echocardiography and/or PK evaluation and based upon the opinion of the Investigator in conjunction with the MyoKardia Medical Monitor.
 
A stress echocardiogram will be administered at Week 48 and Week 72 to evaluate the post-exercise LVOT gradient and to determine whether further dose adjustment may be needed. If the post-exercise LVOT gradient is measured ≥ 50 mmHg, further dose adjustment may be considered and discussed with the MyoKardia Medical Monitor.
 
Dose adjustments beyond the Target Dose may only be exceeded for each given participant following discussion between the Investigator and the MyoKardia Medical Monitor. Lower doses are permissible.
 
The dose will not be increased if one or more of the following criteria are met:
 
• LVEF is $< 55\%$, and/or• LVOT gradient is < 30 mmHg after exercise, and/or• Trough mavacamten plasma concentration is > 350 ng/mL, and/or• A dose increase is not warranted in the clinical judgment of the Investigator 
Dose Reduction Rule: The dose may be reduced or discontinued in the case of an exaggerated pharmacologic effect at any time during the study based on the clinical judgment of the Investigator.
 
Participants who have had a dose adjustment (either in mavacamten or background cardiomyopathy therapy) should return to the clinic approximately 28 days later (± 7 days) for an unscheduled visit with resting TTE to confirm safety. Repeat of post-exercise echocardiographic assessment of LVOT gradient will be at the Investigator's discretion. Based on results and clinical symptoms at follow-up visits, subsequent dose adjustments will be discussed with the MyoKardia Medical Monitor.
 
Temporary Discontinuation: If results as reported by the central laboratories from any visit show mavacamten plasma concentration is ≥ 1000 ng/mL, or LVEF $< 50\%$ (as read by site), or Fridericia-corrected QT interval (QTcF) meets the following criteria, the participant will be notified by the study site/Investigator for further instructions.
 
• If QRS is narrow (< 120 milliseconds), then temporary discontinuation criteria are the smaller of: 15% increase from baseline QTcF OR QTcF ≥ 520 milliseconds• If QRS is wide (≥ 120 milliseconds), then temporary discontinuation criteria are the smaller of: a 15% increase from baseline QTcF OR QTcF ≥ 550 milliseconds 
If the participant is taking 5, 10, or 15 mg, study drug will be temporarily discontinued and he or she will return for an unscheduled visit (with electrocardiogram [ECG] and TTE assessments) 2 to 4 weeks later. If LVEF $\geq 55\%$ (as read by site) and QTcF < 500 milliseconds at the unscheduled visit, then the study drug will be restarted at a lower dose as shown below (previous dose \rightarrow restart dose):

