--	---

	
• 5 mg → resume 5 mg• 10 mg → 5 mg• 15 mg → 10 mg 
Participants on 5 mg who have been temporarily discontinued on treatment based on clinical evaluation can be considered for dose reintroduction at 5 mg following agreement between the Investigator and the MyoKardia Medical Monitor.
 
If LVEF, plasma drug concentration, and/or QTcF persist out of range at the follow-up visit, then the participant will be discontinued from the study.
 
Participants who prematurely discontinue from the PIONEER-OLE study may be considered for rescreening for participation.
 
After Week 6, additional study visits will occur at Week 8 (\pm 7 days), Week 12 (\pm 7 days), and every 12 weeks (\pm 7 days) thereafter. Participants also will be contacted by phone in between clinic visits, at Week 18 and every 12 weeks thereafter. An end of study (EOS) visit will occur 8 weeks (\pm 7 days) after the last administration of study drug. Visits (including the Screening visit which serves as the baseline) will entail recording vital signs, targeted physical examination, ECGs, safety laboratory tests, N-terminal pro B-type natriuretic peptide (NT-proBNP), adverse events (AEs), New York Heart Association (NYHA) functional class, Kansas City Cardiomyopathy Questionnaire (KCCQ) score, and concomitant medications. Predose blood samples for assessment of drug concentration will be obtained at the time points indicated in the Schedule of Assessments. A standard TTE (including but not limited to assessment of LVOT gradient at rest and after Valsalva) will be performed at baseline and at the time points indicated in the Schedule of Assessments. In addition, a stress echocardiogram (with assessment of LVOT gradient post-exercise) will also be performed at baseline and at the time points indicated in the Schedule of Assessments.
 
For females of childbearing potential, pregnancy testing will be performed in clinic or at home every 4 weeks.
 
Participants will be followed through completion of EOS procedures. All AEs, including serious adverse events (SAEs), will be collected from the time of informed consent through the duration of the study, up to and including the Week 260/EOS visit. If there is a significant clinical abnormality or clinically significant laboratory abnormality in need of monitoring, the participant will be followed until resolution of the abnormality or until it is considered stable in the opinion of the Investigator.
 
End of Study (Week 260)
 
Participants who prematurely discontinue the study will attend an early termination visit and return to the study site 8 weeks later for an EOS visit.
 
Participants who complete 252 weeks of mavacamten treatment and do not rollover onto commercially available mavacamten will attend an end of treatment visit and return to the study site 8 weeks later for an EOS visit.

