Dose Reduction Rule: The dose may be reduced or discontinued in the case of an exaggerated pharmacologic effect at any time during the study based on the clinical judgment of the Investigator.

If results as reported by the central laboratories from any visit show mavacamten plasma concentration is ≥ 1000 ng/mL, or LVEF $< 50\%$ (as read by site), or Fridericia-corrected QT interval (QTcF) meets the following criteria, the participant will be notified by the study site/Investigator with further instructions:

- If QRS is narrow (< 120 milliseconds), then temporary discontinuation criteria are the smaller of: 15% increase from baseline QTcF OR QTcF ≥ 520 milliseconds
- If QRS is wide (≥ 120 milliseconds), then temporary discontinuation criteria are the smaller of: a 15% increase from baseline QTcF OR QTcF ≥ 550 milliseconds

Dosing with study drug will be immediately stopped and the following procedures implemented:

- If the participant is taking 5, 10, or 15 mg, study drug will be temporarily discontinued and he or she will return for an unscheduled visit (with electrocardiogram [ECG] and TTE assessments) 2 to 4 weeks later
- If LVEF $\geq 55\%$ (as read by site) and QTcF < 500 milliseconds at the unscheduled visit, then the study drug will be restarted at a lower dose, as shown below (previous dose \rightarrow restart dose):
 - 5 mg \rightarrow resume 5 mg
 - 10 mg \rightarrow 5 mg
 - 15 mg \rightarrow 10 mg

Participants on 5 mg who have been temporarily discontinued on treatment based on clinical evaluation can be considered for dose reintroduction at 5 mg following agreement between the Investigator and the MyoKardia Medical Monitor.

If LVEF (as read by site), plasma drug concentration, and/or QTcF persist out of range at the follow-up visit, then the participant will be discontinued from the study.

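### The restart rule uses only a fixed QTcF limit, so at baselines below 434.8 ms drug can be restarted while the hold rule is still met

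*Combined protocol and SAP*

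**What the plan says.** The rules are in protocol Section 4 (Dose Reduction Rule) and are repeated in the Synopsis under Temporary Discontinuation.

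**Hold.** The trigger begins "If results as reported by the central laboratories from any visit show mavacamten plasma concentration is" at or above 1000 ng/mL. The alternatives are a site-read LVEF below 50% or a QTcF limit. For narrow QRS (below 120 ms) the "temporary discontinuation criteria are the smaller of: 15% increase from baseline QTcF OR QTcF" of 520 ms or more; for wide QRS the cap is 550 ms.

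**Follow-up visit.** The participant "will return for an unscheduled visit (with electrocardiogram [ECG] and TTE assessments) 2 to 4 weeks later".

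**Restart.** The test is LVEF of at least 55% together with "QTcF < 500 milliseconds at the unscheduled visit, then the study drug will be restarted at a lower dose". The steps are 15 mg to 10 mg, 10 mg to 5 mg, and 5 mg back to 5 mg. For participants on 5 mg held on clinical evaluation, a further sentence says they "can be considered for dose reintroduction at 5 mg following agreement between the Investigator and the MyoKardia Medical Monitor".

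**Removal.** The last sentence covers LVEF as well as the other two measures: if "plasma drug concentration, and/or QTcF persist out of range at the follow-up visit, then the participant will be discontinued from the study". The range is not defined.

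Section 5.5.1 says treatment is discontinued for systolic dysfunction, higher than expected concentration or excessive QT prolongation, and refers to Section 7.5. Section 7.5 repeats the triggers and refers back to Section 4 for the procedures.

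**The concern.** The hold rule is relative to each participant's baseline; the restart rule is not. For LVEF, restart is stricter than hold (55% against 50%), which gives a margin of recovery before re-exposure. For QTcF the same margin exists only at higher baselines. At lower baselines the order reverses, and a participant can qualify for restart without having fallen below the limit that stopped treatment.

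The restart test also omits concentration, although concentration is both a ground for holding and a ground for removal.

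The primary objective is long-term safety, and Section 1.3 lists arrhythmia due to QT prolongation as a potential risk. A site that applies the restart sentence as written could re-expose someone who still meets the stop rule. Another site could keep an identical participant off drug. The step down in dose gives no protection at 5 mg, which is everyone's starting dose and the Target Dose for 6 of the 20 entries in Table 1.

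**Working it through.** The protocol states no figure on this point to reproduce; the check is threshold algebra.

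**Inputs**
- Hold limit (Section 4): H = min(1.15b, 520) for narrow QRS and min(1.15b, 550) for wide QRS, where b is baseline QTcF in ms. A 15% increase is read as 15% or more.
- Restart (Section 4): QTcF < 500 ms, with LVEF of at least 55%.
- Entry (Section 5.3): QTcF above 500 ms is excluded. No lower bound or baseline distribution is given, so the baselines below are assumptions.

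**Overlap.** Both rules are met when H ≤ QTcF < 500. Both caps exceed 500, so QRS width drops out and the condition is 1.15b ≤ QTcF < 500. This needs b < 500/1.15 = 434.8 ms.

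| Assumed baseline (ms) | 1.15b (ms) | Follow-up QTcF meeting both rules (ms) | Whole-ms values | Of these, rise > 60 ms | Rise at 499 ms |
|---|---|---|---|---|---|
| 380 | 437.0 | 437 to 499 | 63 | 59 | 119 ms (31.3%) |
| 400 | 460.0 | 460 to 499 | 40 | 39 | 99 ms (24.8%) |
| 420 | 483.0 | 483 to 499 | 17 | 17 | 79 ms (18.8%) |
| 430 | 494.5 | 495 to 499 | 5 | 5 | 69 ms (16.0%) |
| 434.8 or more | 500 or more | none | 0 | 0 | not applicable |

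Example: baseline 420 ms, follow-up 490 ms, LVEF at least 55%. The rise is 70 ms, or 70/420 = 16.7%. Since 490 ≥ 483, the hold rule is met; since 490 < 500, the restart rule is met.

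**Clinical scale.** Because 0.15b ≥ 60 when b ≥ 400, every overlap value at baselines of 400 ms or more is a rise of at least 60 ms. The top QTcF change category in Section 11.3.8.2 is above 60 ms.

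**Does the removal sentence settle it?** There are two readings of the undefined range.
- *Hold limits.* The 490 ms ECG above calls for restart under one sentence and removal under the other. Values from 500 ms up to H (for example 500 to 505 ms at baseline 440, where H = 506) and LVEF of 50 to 54% meet neither sentence.
- *Restart limits.* Restart and removal no longer conflict on LVEF or QTcF, and those intermediate values lead to removal. But the 490 ms participant restarts while the any-visit hold rule is still met.

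The mismatch between hold and restart survives both readings.

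**Concentration.** If a level is measured at follow-up and is still at or above 1000 ng/mL, with LVEF at least 55% and QTcF below 500 ms, the restart sentence is satisfied even though the removal sentence names concentration. Section 4 names only ECG and TTE for that visit.

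**Check of the remedy.** With restart requiring QTcF < min(500, 1.15b), a grid over whole-ms baselines from 350 to 500 ms finds no value that meets both rules, for either QRS class.

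**The case against.** The strongest reply is that the text, read as a whole, already leans towards caution. The removal sentence comes last, applies to the same visit and names all three measures. Section 5.5.1 points towards stopping, and the hold rule covers any visit, including this one. Participants on 10 or 15 mg restart one step lower. The 5 mg sentence brings in the Medical Monitor, and Table 2 footnote a says dosing does not resume until the site notifies the participant. A dose adjustment calls for a visit about 28 days later, and Section 9.3.3 lets the Investigator add ECGs.

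Much of this stands as mitigation, and a careful site may well do the right thing. But none of it says which mandatory sentence prevails, and Section 5.5.1 leads through Section 7.5 back to Section 4. The 28-day visit names a resting TTE, not an ECG.

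Three stronger claims might be inferred, and the documents do not support them:
- *The protocol orders restart and removal on the same ECG.* That is so only if the range means the hold limits. The claim that intermediate values have no stated next step rests on the same reading.
- *No drug level is drawn at follow-up.* Table 2 footnote a refers unscheduled visits to Table 3, whose grid is missing from the available text, and allows laboratory tests at such visits.
- *Participants will be restarted with rises near 119 ms.* That figure needs an assumed baseline of 380 ms and a follow-up value of 499 ms after 2 to 4 weeks off drug. At that baseline, 14 of the 63 overlap values (437 to 450 ms) do not reach the lowest QTcF category in Section 11.3.8.2, above 450 ms. The categories are for tabulation and are not stopping limits.

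**Conclusion.** The point holds as an inconsistency between two safety rules, and it should be fixed. For baselines below 434.8 ms, the written restart test admits QTcF values that still meet the hold test, and precedence is not stated. The text and the arithmetic are certain. Reading the increase as strictly more than 15% would move the lower end of the overlap by at most 1 ms (461 instead of 460 at baseline 400).

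The practical consequence is uncertain. It depends on how many participants have baselines below 434.8 ms, how many are held, and how sites read the removal sentence. The documents do not settle these points, and the number affected may be zero.

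The concentration gap is the weaker part: the removal sentence covers it in part, and whether a level is taken cannot be checked. The study has no hypothesis test or powered sample size (Section 11.1), so no inference is affected.

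**What to change.** In Section 4 and the Synopsis, allow restart only if all of these hold:
- LVEF is at least 55%.
- QTcF is below 500 ms and below the participant's own baseline- and QRS-specific hold limit.
- Concentration is below 1000 ng/mL, where the hold was for concentration or a level is available.

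Define the out-of-range wording to match these limits. If Table 3 does not already provide a PK sample at the 2-to-4-week visit, add one for participants held for concentration.

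Two matters are policy choices for the sponsor, and either answer is workable once written down: what happens to intermediate values, and whether a persisting value means removal from the study or a longer hold.

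The cost is a change of wording in two places and at most one blood draw at a visit that already takes place. Some participants would stay off drug longer, including while a PK result is awaited. Sample size, endpoints and visit schedule do not change.

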1.3. Known and Potential Benefits and Risks

In nonclinical studies, safety testing in other mammalian species has demonstrated that dose-limiting toxicity is related to exaggerated pharmacologic effect and not to off-target adverse effects. Experiments with isolated adult rat ventricular myocytes in vitro and with anesthetized

rats in vivo have established that the pharmacological effects of mavacamten may be counteracted by positive inotropes (isoproterenol, dobutamine, or levosimendan).

Of the 18 clinical studies of mavacamten to date, clinical study reports are available for 15 studies. Overall, mavacamten appears well-tolerated with little evidence for off-target toxicity. In participants with oHCM, the clinical benefits of mavacamten treatment in the extension study (MAVA-LTE), which relies exclusively on clinical measures of cardiac function (including site-read echocardiographic measures) and participants' symptoms to guide dose titration, are consistent with the EXPLORER-HCM parent study, in which dose optimization was guided in part by plasma drug concentrations, specifically:

- reduced LVOT gradients
- improved New York Heart Association (NYHA) class
- improved diastolic function
- decreased left atrial volume index
- reduced wall stress (as measured by N-terminal pro B-type natriuretic peptide [NT-proBNP])

The known risks of mavacamten use from available nonclinical and/or clinical data to date include dizziness and cardiac failure due to systolic dysfunction (symptomatic left ventricular ejection fraction [LVEF] < 50%). Systolic heart failure is due to mavacamten's exaggerated on-target effect of reduction in cardiac contractility (ie, reduced LVEF). Potential risks of mavacamten use include embryofetal toxicity (observed in animal studies only), heart failure due to interaction with cytochrome (CYP) 2C19 and potent 3A4 inhibitors, and arrhythmia due to QT prolongation (observed in animal species and healthy volunteers).

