For participants who do not withdraw consent for ongoing study participation but fail to return to the site, the Investigator should make every effort to contact the participant (eg, contacting participant's family or private physician, reviewing available registries or health care databases) and to determine the participant's health status, particularly vital status. Attempts to contact such participants must be documented in the participant's records (eg, number of attempts and dates of attempted telephone contact and receipt for sending a registered letter).

Participants who have withdrawn from the study cannot be treated further in the study. Their study identification numbers must not be reused.

Treatment Discontinuation

The Investigator should discontinue a participant's study treatment permanently for any of the following reasons:

- Pregnancy

- Heart failure related to systolic dysfunction
- Study termination
- Study site termination by MyoKardia (eg, in the case of major, noncorrectable protocol deviations)
- Undergoing septal reduction therapy
- Participant withdrawal from treatment or withdrawal from study

Study treatment will be discontinued in the case of exaggerated pharmacologic effect (systolic dysfunction), higher than expected plasma concentration, or excessive QT prolongation (see [Section 7.5](#)).

In addition, study treatment may be temporarily discontinued in the case of an AE or SAE at the Investigator's discretion if there is a safety concern.

In all cases, the reason(s) for permanent treatment discontinuation or study withdrawal will be recorded in the source document and on the appropriate eCRF.

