7.4.3. Criteria for Rechallenge of Mavacamten After Potential Hepatotoxicity

The decision to rechallenge the participant should be discussed and unanimously agreed upon by the Investigator and Sponsor.

If signs or symptoms recur with rechallenge, then mavacamten will be permanently discontinued. Participants who clearly meet the criteria for permanent discontinuation (as described in [Section 7.4.1](#)) should never be rechallenged.

7.5. Guidelines for the Management of Exaggerated Pharmacologic Effect (Systolic Dysfunction), Excessive QT Prolongation, or Higher Than Expected Plasma Concentration

If results, as reported by the central laboratories from any visit, show mavacamten plasma concentration is ≥ 1000 ng/mL, or LVEF $< 50\%$ (as read by site), or QTcF meets the following criteria, the participant will be notified by the study site/Investigator for further instructions.

- If QRS is narrow (< 120 milliseconds), then temporary discontinuation criteria are the smaller of: 15% increase from baseline QTcF OR QTcF ≥ 520 milliseconds.
- If QRS is wide (≥ 120 milliseconds), then temporary discontinuation criteria are the smaller of: a 15% increase from baseline QTcF OR QTcF ≥ 550 milliseconds.

It will be communicated to the Investigator and Sponsor that a stopping criterion has been met and the procedures outlined in [Section 4](#) will be implemented. If a participant discontinues study drug permanently, the participant will be encouraged to undergo ET and EOS assessments.

Any participant who experiences heart failure related to systolic dysfunction will be managed as per site-specific standard of care.

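### After systolic heart failure, Section 5.5.1 ends treatment but Section 4 restarts the drug if LVEF and QTcF recover, and no sentence says which rule governs

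*Combined protocol and SAP*

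**What the plan says.** **Permanent stop.** Section 5.5.1 (Treatment Discontinuation) tells the Investigator to discontinue "study treatment permanently for any of the following reasons", and one listed reason is "Heart failure related to systolic dysfunction". A separate sentence after the list reads "Study treatment will be discontinued in the case of exaggerated pharmacologic effect (systolic dysfunction"). That sentence also covers high plasma concentration and QT prolongation, points to Section 7.5, and does not say whether the discontinuation is temporary or permanent.

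**Hold and restart.** In Section 4, a site-read LVEF below 50% triggers a temporary hold and an unscheduled visit 2 to 4 weeks later. If LVEF is then at least 55% and "QTcF < 500 milliseconds at the unscheduled visit, then the study drug will be restarted at a lower dose, as shown below", dosing resumes by a fixed map: 5 mg to 5 mg, 10 mg to 5 mg, 15 mg to 10 mg. The Synopsis repeats the rule: "then the study drug will be restarted at a lower dose as shown below". If LVEF, plasma concentration or QTcF remains out of range, the participant is discontinued from the study.

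**Routing.** Section 7.5 uses the same triggers and says "It will be communicated to the Investigator and Sponsor that a stopping criterion has been met and the procedures outlined in" Section 4 are to be carried out. Its one sentence on heart failure is "Any participant who experiences heart failure related to systolic dysfunction will be managed as per site-specific standard of care".

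**Meaning of the event.** Section 1.3 lists as a known risk "cardiac failure due to systolic dysfunction (symptomatic left ventricular ejection fraction [LVEF] < 50"%). Section 11.2.1 defines the heart failure safety endpoint in the same terms.

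**The concern.** The two triggers overlap, and in one outcome the two actions are opposite. Site staff handling a low LVEF would work from Section 4, the Synopsis or Section 7.5. None of these mentions Section 5.5.1 or makes heart failure an exception to restart. A site that follows Section 4 as written would re-expose a participant after an on-target harm that the protocol already names as a known risk. A site that follows Section 5.5.1 would not. What is at stake is that participant's safety and consistent handling across up to 5 sites.

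**Working it through.** The plan gives no figure on this point, so the check sets the rules side by side.

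1. **Do the triggers overlap?** The hold trigger is site-read LVEF < 50%, whatever the symptoms. Section 9.1.1 also states the stopping criterion by LVEF alone. The permanent-stop trigger is heart failure related to systolic dysfunction, described in Sections 1.3 and 11.2.1 as symptomatic LVEF < 50%. On that description, symptomatic site-read LVEF < 50% is a subset of LVEF < 50%, so such a participant meets both rules.

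2. **Do the actions differ?** It depends on what the return visit shows:

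| At the hold | At the return visit | Section 5.5.1 | Section 4 | Conflict |
|---|---|---|---|---|
| LVEF < 50%, no heart failure | LVEF ≥ 55%, QTcF < 500 ms | Heart failure item not met; points to 7.5 | Restart | No |
| LVEF < 50%, heart failure | A stopping parameter still out of range | Permanent stop | Discontinued from study | No |
| LVEF < 50%, heart failure | LVEF ≥ 55%, QTcF < 500 ms | Permanent stop | Restart at 5 mg (from 5 or 10 mg) or 10 mg (from 15 mg) | **Yes** |

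3. **Illustrative case (assumed values).** A participant on 10 mg develops heart failure symptoms with site-read LVEF 45%. After 3 weeks off drug, LVEF is 57% and QTcF is 450 ms. Under Section 5.5.1 treatment has ended. Under Section 4, 57 ≥ 55 and 450 < 500, so the drug is restarted at 5 mg. Neither restart condition concerns symptoms, and ECG and TTE are the only assessments named for that visit.

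4. **Does any sentence rank the rules?** Section 4 does not cite Section 5.5.1. Section 7.5 sends a met stopping criterion to Section 4, and its heart failure sentence covers clinical management without addressing study drug. The verbs do not settle it either: the permanent list says what the Investigator *should* do, while the restart rule uses *will*.

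5. **Does the protocol write such a ranking elsewhere?** Yes, for liver injury. Section 7.4.2 limits conditional withholding to participants outside the permanent criteria, and Section 7.4.3 rules out rechallenge for those who clearly meet them. Systolic heart failure has no equivalent sentence.

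**The case against.** The strongest reply is that an ordinary reading already resolves this. Section 5.5.1 puts heart failure in the permanent list and systolic dysfunction in a separate sentence pointing to Section 7.5. That looks like two tiers: heart failure ends treatment, and a fall in LVEF without it follows hold-and-restart. The restart text concerns temporary discontinuation, and someone stopped permanently is no longer on that path. Restart also has no exception for pregnancy or septal reduction, and few would read Section 4 as overriding those. Section 5.5.1 does not itself define heart failure, so the judgement is the Investigator's, and an Investigator who has made it has a direct instruction. This is good evidence of intent. It remains an inference from layout, and the sections that staff would act on do not carry it.

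There are also real safeguards:

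- The Investigator may reduce or stop the dose at any time for an exaggerated effect.
- The Sponsor, as well as the Investigator, is told when a stopping criterion is met.
- After a dose adjustment the participant returns at about 28 days for a resting TTE, and subsequent adjustments are discussed with the Medical Monitor. A lower-dose restart is plausibly such an adjustment, but this check comes after the restart.
- Reintroduction at 5 mg after a hold based on clinical evaluation needs Medical Monitor agreement.
- Table 2 footnote a has dosing wait for notice from the site.

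These lower the chance of an unwanted restart. None names heart failure as a bar to it.

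A reader might infer that a heart failure event would reach the table of TEAEs leading to permanent discontinuation only if Section 5.5.1 is applied. The documents do not support that. Section 4 also ends participation when values stay out of range, and the Investigator can discontinue under the Dose Reduction Rule. Heart failure is in any case a separate safety endpoint in Section 11.2.1, so the event is not lost.

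**Conclusion.** Wrong as written: two safety rules conflict. The conflict is limited to participants who have heart failure related to systolic dysfunction with site-read LVEF < 50%, and who then reach LVEF ≥ 55% with QTcF < 500 ms at the 2-to-4-week visit. For them one section ends treatment and another restarts it. Low LVEF without heart failure, and LVEF that stays out of range, raise no conflict.

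No rate can be given, because the documents do not say how many participants will meet both rules and then recover. A reader might take the spread of Target Doses in Table 1 as a measure of how many are exposed. It describes planned dosing for everyone and says nothing about who develops heart failure or recovers. Nor do the documents support reading Section 4 as deliberately overriding Section 5.5.1, since the layout of Section 5.5.1 points the other way.

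The conclusion assumes that heart failure in Section 5.5.1 carries the meaning given in Sections 1.3 and 11.2.1, or at least that the Investigator's heart failure judgement can coincide with a site-read LVEF below 50%. It should be corrected because the restart rule, followed literally, can give the wrong action after a known drug harm.

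**What to change.** Add the same statement to the Synopsis, Section 4 and Section 7.5:

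> If the Investigator judges that heart failure related to systolic dysfunction has occurred, treatment is permanently discontinued under Section 5.5.1 and the restart rule does not apply; hold-and-restart for LVEF < 50% applies only in the absence of heart failure.

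Leave the Section 5.5.1 trigger and the Section 11.2.1 endpoint definition as they are. This follows the pattern the protocol already uses for liver injury.

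The cost is one short statement in three places, with no new visits, assessments or endpoint changes. Section 13.4 allows an Administrative Letter for nonsubstantial clarifications and corrections of inconsistencies; whether this qualifies is for the sponsor to decide. The downside is that a participant with heart failure whose LVEF recovers loses the option of restarting, which Section 5.5.1 already appears to intend.
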